## 2.2 Rationale

The goal of this study is to demonstrate the ability of a biomarker test to identify a patient population in which antibacterial treatment provides no clear benefit. This study will provide critical information to curtail the empiric use of antibiotics in a disease area of high antibacterial use – non-pneumonia LRTI, which includes tracheitis, tracheobronchitis, acute bronchitis, acute asthma exacerbation, and acute exacerbation of chronic obstructive pulmonary disease (AECOPD). In these cases, antibiotics are frequently prescribed without proper rationale leading to avoidable adverse events and driving antibacterial resistance. The vast majority of acute non-pneumonia LRTIs presenting in outpatient settings are suspected to be of viral etiology; however, most of these cases are still treated with antibiotics. Implementation of diagnostics, such as host biomarker-based tests, to inform antibiotic use could reduce unnecessary antibiotic prescriptions. The present study focuses on patients with low PCT levels, suggesting the absence of a bacterial infection and tests the hypothesis that antibiotics can safely be withheld in this population.

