8.2.4. Sensitivity Analysis of Clinical Improvement, ITT Analysis Population

Robustness of the multiple imputation model for ITT analysis population will be assessed by using tipping point analysis using linear regression as described in Section 8.2.1 using linear regression adjusting for treatment group and centered study day of D5V (or D11V, D28V). A point estimate of the difference in rates of clinical improvement, placebo relative to azithromycin and its 95% CI from the linear regression model will be reported. The results of this sensitivity analyses will be provided in [Table 27](#) for D5V, [Table 28](#) for D11V and [Table 29](#) for D28V.

8.2.5. Analysis of Number of Days of Antibiotics Use at D11V and D28V Using ATP Analysis Populations

Using the ATP-11 and ATP-28 analysis populations, respectively, the mean number of days of antibiotic use from Day 1 until D11V or D28V will be computed based on the definitions from Section 6.5.5 for the placebo group and the azithromycin group, in addition to an estimated difference in means for the placebo group relative to the azithromycin group using the t-test and its associated 95% CIs calculated based on t-test. The significance of the difference in means will be tested by a t-test and results from the Satterthwaite method will be provided in [Table 30](#) and [Table 31](#). An individual listing of days of antibiotics use is provided in [Listing 16](#).

8.2.6. Analysis of Medically Attended Events at D11V and D28V Using ATP Analysis Populations

Proportions of subjects with one or more return visits to a physician's office or urgent care, one or more emergency department visits, or one or more hospitalizations for persistent or worsening LRTI at any time after randomization by D11V or D28V will be produced for D11V and D28V and results will be reported in [Table 32](#), [Table 33](#), and [Table 34](#). Tests for differences in proportions, placebo relative to azithromycin, will be given by Fisher's Exact Test. In addition, an estimated odds ratio and its associated 95% CI calculated using the Wald Method will be provided. [Listing 19](#) contains all medically attended visits while [Listing 20](#) provides a listing of all hospitalizations.

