8.2.9. Analysis of Solicited Events at D5V Using ATP-5 Analysis Population

Results of the analysis of solicited events at D5V, a component of DOOR, will be presented using forest plots of 95% CIs for the risk difference of each solicited event and the risk difference for placebo compared to azithromycin of any solicited event, for each severity threshold (mild or greater, moderate or greater, or severe) in [Figure 2](#), [Figure 3](#), and [Figure 4](#). Results will also be reported in tables [Table 56](#), [Table 57](#), and [Table 58](#). Tests for differences in proportions between treatment arms will be given by Fisher's exact tests. Since Fisher's test cannot be inverted, there is no corresponding CI. Therefore, the Miettinen-Nurminen method will be used to compute all 95% CIs for risk differences. Note that the CI results might not be consistent with the p-value from Fisher's exact test.

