8.3.5. Analysis of Medically Attended Events at D11V Using ATP-11 Analysis Populations

A forest plot of 95% CIs for the risk difference for placebo compared to azithromycin of one or more visits to an ED, one or more visits to an outpatient clinic, or one or more visits to an urgent care center or one or more hospitalizations for persistent or worsening LRTI at any time after randomization will be produced for D11V using ATP-11 analysis population in [Figure 9](#) and results will also be presented in [Table 44](#) to include a p-value from Fisher's exact test. The Miettinen–Nurminen method will be used to compute all 95% CIs for risk differences.

8.3.6. Improvement in Qualifying Symptoms or Vital Signs at D11V Using ATP-11 Analysis Population

The proportions of subjects exhibiting improvement in any symptom, any symptom or fever, at least two symptom, and one qualifying symptom (cough, sputum production, chest pain, or difficulty breathing) or fever at D11V compared to baseline will be computed for placebo versus azithromycin along with associated 95% CIs using ATP-11 population. A forest plot of 95% CIs for the difference for placebo compared to azithromycin in proportions of subjects with improvement any symptom or fever, any symptom, each individual symptom or fever will be provided in [Figure 11](#). Results will also be reported in [Table 35](#), and tests for differences in proportions between treatment arms will be given by Fisher's exact tests. The Miettinen–Nurminen method will be used to compute all 95% CIs for risk differences for placebo compared to azithromycin.

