Table 28: Sensitivity Analysis of Clinical Improvement at D11V - ITT Analysis Population

Table 29: Sensitivity Analysis of Clinical Improvement at D28V - ITT Analysis Population

Table 30: Analysis of the Number of Days of Antibiotics Use - ATP-11 Analysis Population

Statistic	Value
Number of days of Antibiotic Use – Mean (95% CI)	
Azithromycin (N=X)	x.x (x.x, x.x)
Placebo (N=X)	x.x (x.x, x.x)
Difference in Means, placebo relative to azithromycin (95% CI) ^a	xx.x (xx.x, xx.x)
P-value ^b	x.xxx
Note: N = Number of subjects in the ATP-11 population in the corresponding treatment group. ^a The difference in means was calculated with azithromycin being the reference and its 95% CI based on t-test. ^b P-value obtained by t-test.	

Table with similar format:

Table 31: Analysis of the Number of Days of Antibiotics Use - ATP-28 Analysis Population

[Implementation Note: Update the footnote to use ATP-28.]

Table 32: Analysis of One or More Return Visits to a Physician's Office or Urgent Care for Persisting or Worsening LRTI

Analysis Population	Statistic	Value
ATP-11	Subjects with one or more return visit to a physician's office or urgent care by D11V – n (%)	
	Azithromycin (N=X)	x (xx)
	Placebo (N=X)	x (xx)
	Odds Ratio, placebo relative to azithromycin (95% CI) ^a	x.x (x.xx, x.xx)
	P-value ^b	x.xxx
ATP-28	Subjects with one or more return visit to a physician's office or urgent care by D28V – n (%)	
	Azithromycin (N=X)	x (xx)
	Placebo (N=X)	x (xx)
	Odds Ratio, placebo relative to azithromycin (95% CI) ^a	x.x (x.x, x.x)
	P-value ^b	x.xxx
N = Number of subjects in the respective analysis population and treatment group. ^a 95% CI for the odds ratio calculated using the Wald method. ^b P-value obtained by Fisher's Exact Test.		

Table 33: Analysis of One or More Emergency Department Visits for Persisting or Worsening LRTI

Analysis Population	Statistic	Value
ATP-11	Subjects with one or more emergent department visits by D11V – n (%)	
	Azithromycin (N=X)	x (xx)
	Placebo (N=X)	x (xx)
	Odds Ratio, placebo relative to azithromycin (95% CI) ^a	x.x (x.x, x.x)
	P-value ^b	x.xxx
ATP-28	Subjects with one or more emergent department visits by D28V – n (%)	
	Azithromycin (N=X)	x (xx)
	Placebo (N=X)	x (xx)
	Odds Ratio, placebo relative to azithromycin (95% CI) ^a	x.x (x.x, x.x)
	P-value ^b	x.xxx

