
N = Number of subjects in the respective analysis population and treatment group. ^a95% CI for the odds ratio calculated using the Wald method. ^bP-value obtained by Fisher’s Exact Test.
		

Table 34: Analysis of One or More Hospitalizations for Persisting or Worsening LRTI at Any Time After Randomization

Analysis Population	Statistic	Value
ATP-11	Subjects with one or more hospitalizations by D11V – n (%)	
	Azithromycin (N=X)	x (xx)
	Placebo (N=X)	x (xx)
	Odds Ratio, placebo relative to azithromycin (95% CI) ^a	x.x (x.x, x.x)
	P-value ^b	x.xxx
ATP-28	Subjects with one or more hospitalizations by D28V – n (%)	
	Azithromycin (N=X)	x (xx)
	Placebo (N=X)	x (xx)
	Odds Ratio, placebo relative to azithromycin (95% CI) ^a	xx.x (xx.x, xx.x)
	P-value ^b	x.xxx

N = Number of subjects in the respective analysis population and treatment group. Only subjects not hospitalized at enrollment or randomization visit will be included.
 
^a95% CI for the odds ratio calculated using the Wald method.
 
^bP-value obtained by Fisher's Exact Test.
		

Table 35: Improvement in LRTI Symptoms or Fever at D11V - ATP-11 Analysis Population

Symptom	Azithromycin				Placebo				Difference (95% CI) ^b	Odds Ratio (95% CI) ^c	P-Value ^d
	N	n	%	95% CI ^a	N	n	%	95% CI ^a			
Any Symptom	x	x	x	(x.x, x.x)	x	x	x	(x.x, x.x)	xx (x.x, x.x)	x.x (x.x, x.x)	x.xxx
Any Symptom or Fever	x	x	x	(x.x, x.x)	x	x	x	(x.x, x.x)	xx (x.x, x.x)	x.x (x.x, x.x)	x.xxx
At Least 2 Symptoms or Fever	x	x	x	(x.x, x.x)	x	x	x	(x.x, x.x)	xx (x.x, x.x)	x.x (x.x, x.x)	x.xxx
Cough	x	x	x	(x.x, x.x)	x	x	x	(x.x, x.x)	xx (x.x, x.x)	x.x (x.x, x.x)	x.xxx
Sputum Production	x	x	x	(x.x, x.x)	x	x	x	(x.x, x.x)	xx (x.x, x.x)	x.x (x.x, x.x)	x.xxx
Chest Pain	x	x	x	(x.x, x.x)	x	x	x	(x.x, x.x)	xx (x.x, x.x)	x.x (x.x, x.x)	x.xxx
Difficulty Breathing	x	x	x	(x.x, x.x)	x	x	x	(x.x, x.x)	xx (x.x, x.x)	x.x (x.x, x.x)	x.xxx
Fever	x	x	x	(x.x, x.x)	x	x	x	(x.x, x.x)	xx (x.x, x.x)	x.x (x.x, x.x)	x.xxx

N = Number of subjects in the ATP-11 analysis population and the respective treatment group with the symptom of severity of grade 1 or worse symptom or with fever at baseline.
n = Number of subjects with improvement.
^a95% CI for proportions calculated using the Wilson method.
^b95% CI for the difference in proportions, placebo relative to azithromycin, calculated using the Miettinen–Nurminen method.
^c95% CI for the odds ratio, placebo relative to azithromycin, calculated using the Wald method.
^dP-values obtained by Fisher’s Exact Test.

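### At Day 28, return visits, ED visits and hospitalisations are compared only by a Fisher p-value and a Wald odds-ratio interval that does not exist if either arm has no event; the SAP's own risk-difference interval should be added

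*SAP*

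**What the plan says.** SAP 8.2.6 covers return visits to a physician's office or urgent care, ED visits, and hospitalisations for persistent or worsening LRTI, by D11V and by D28V. "Tests for differences in proportions, placebo relative to azithromycin, will be given by Fisher's Exact Test", and "an estimated odds ratio and its associated 95% CI calculated using the Wald Method will be provided". The shells of Tables 32 to 34 follow this. Under a row label such as "Subjects with one or more hospitalizations by D28V" in Table 34 they show n (%) for each arm, an odds ratio and a p-value, with the footnote "95% CI for the odds ratio calculated using the Wald method". There is no risk-difference row, and nothing says what to do when a cell is zero. Protocol 11.4.2, items 5 to 7, asks for proportions, an odds ratio with a 95% interval and Fisher's test in ATP-11 and ATP-28, and does not name the interval method.

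The SAP treats the same kinds of event differently at earlier visits. At D5V (8.2.10, Table 43) and D11V (8.3.5, Table 44) it plans risk differences, and the Miettinen-Nurminen method "will be used to compute all 95% CIs for risk differences". At D28V that method is planned for symptom improvement: Table 36 takes the layout of Table 35, which shows a Miettinen-Nurminen difference, a Wald odds ratio and a Fisher p-value side by side.

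**The concern.** Protocol 2.2 says that the study "tests the hypothesis that antibiotics can safely be withheld in this population". Admissions and ED visits through the last follow-up visit bear directly on that, and for them the useful quantity is how large an excess on placebo the data still allow. The Wald interval for an odds ratio cannot give this when an arm has no event, which is when a rare outcome most needs a bound. Tables 32 to 34 would then hold two percentages and a p-value.

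Sparse counts are plausible for hospitalisation at least. An event counts only if it is for persistent or worsening LRTI, which the SAP's derivation ties to a non-study antibiotic given for LRTI (6.5.2.3), and the analysis is limited to subjects who took all five doses (6.3).

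**Working it through.** **Inputs.** The documents give no event rate for these outcomes and no size for ATP-28. The nearest figure is ATP-5: 674 randomised with 16.9% loss leaves 674 × (1 − 0.169) = 560, or 280 per arm (SAP 5 and 6.6). I assume 280 per arm at D28V and show 240 to 337, where 337 is everyone randomised to an arm. Event rates are assumptions throughout.

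**Step 1: when the planned interval exists.** With a and c events and b and d non-events in the two arms, the Wald interval is exp{ln(ad/bc) ± 1.96 √(1/a + 1/b + 1/c + 1/d)}. If a or c is zero, one term is 1/0 and there is no interval.

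**Step 2: how often that happens.** With n per arm and rate p in both arms, the chance that at least one arm is empty is 1 − [1 − (1 − p)^n]². At n = 280:

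- p = 0.5%: 0.995^280 = 0.246, so 1 − 0.754² = 43% (51% at 240 per arm, 34% at 337).
- p = 1%: 0.99^280 = 0.060, so 1 − 0.940² = 12% (17% at 240, 7% at 337).
- p = 2%: 0.98^280 = 0.0035, so 1 − 0.9965² = 0.7%.

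With unequal rates (azithromycin v placebo) at 280 per arm the chance is 53% for 0.25% v 1%, 25% for 0.5% v 2%, and 6% for 1% v 3%.

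**Step 3: one example, 5/280 placebo v 0/280 azithromycin.** The Fisher p-value is 2 × (280·279·278·277·276)/(560·559·558·557·556) = 0.061. The Wald interval does not exist. The risk difference is 5/280 = 1.79 points. The Miettinen-Nurminen interval is the set of differences that the score test does not reject. At a difference of zero the pooled rate is 5/560 = 0.00893, the standard error is √[0.00893 × 0.99107 × (2/280) × (560/559)] = 0.00796, and z = 0.01786/0.00796 = 2.24. Zero is therefore just outside the interval, which is 0.42 to 4.11 points.

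**Step 4: other sparse results at 280 per arm.**

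| Events, placebo v azithromycin | Fisher p | Odds ratio (Wald 95% CI) | Difference in points (Miettinen-Nurminen 95% CI) |
|---|---|---|---|
| 0 v 0 | 1.000 | none | 0.00 (−1.36 to 1.36) |
| 3 v 0 | 0.249 | none | 1.07 (−0.29 to 3.10) |
| 5 v 0 | 0.061 | none | 1.79 (0.42 to 4.11) |
| 5 v 1 | 0.216 | 5.07 (0.59 to 43.70) | 1.43 (−0.39 to 3.80) |
| 8 v 3 | 0.222 | 2.72 (0.71 to 10.34) | 1.79 (−0.61 to 4.60) |

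The risk difference gives a finite upper bound in every row. With only one event in an arm the Wald interval exists but is very wide.

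**The case against.** The case for leaving the tables alone has real parts.

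- **These are supportive analyses.** SAP 8.1.1 rests the conclusion on the primary analysis alone, and nowhere treats p > 0.05 as evidence of safety. That stands, and it limits the weight of the point.
- **Day 28 harm is visible elsewhere.** Tables 32 to 34 give n (%), so a reader can derive a difference. Listings 19 and 20 show each visit and admission. Table 49 gives the D28V ordinal levels by arm in ITT with Wilson intervals, and these events count as failures in D28V clinical improvement. It would be wrong to infer that Day 28 harm goes unreported. However, none of these is a pre-specified interval for the between-arm difference in each event type.
- **An empty arm is not likely for every outcome.** The population includes asthma and COPD exacerbations, and office or urgent-care visits may be common enough that the Wald interval nearly always exists. This also stands.

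A reader might infer more than the documents support:

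- **That Fisher's test would usually miss even a tripled rate on placebo.** This depends on the base rate. At 280 per arm its power is 28% for 1% to 3%, but 62% for 2% to 6% and 82% for 3% to 9%. Nor does the 80% power target apply here: it belongs to the Day 5 primary endpoint.
- **That an exact conditional odds-ratio interval should replace Wald.** For 5 v 0 it runs from 0.92 to infinity, so it gives no upper bound in the sparse case.
- **That the remark that Fisher's "test cannot be inverted, there is no corresponding CI" undermines these tables.** The wording is loose, since Fisher's test does invert to an odds-ratio interval. But it stands in SAP 8.2.9 to 8.2.13, where it explains the choice of a risk-difference interval. Removing it would change nothing in Tables 32 to 34.

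**Conclusion.** The point holds for D28V. Each of the three event types has n (%), a Fisher p-value and a Wald odds-ratio interval, and the interval is missing whenever an arm has no event. At an assumed 280 per arm that has about a 43% chance at a 0.5% rate in each arm, 12% at 1% and under 1% at 2%. It is therefore mainly a matter for rare outcomes, of which hospitalisation is the likeliest. The rates and the ATP-28 size are assumptions, and 240 to 337 per arm does not alter the picture.

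In the 5 v 0 example, p=0.061 and an interval that excludes zero do not show Fisher's test to be wrong. SAP 8.2.9 already warns that the two methods can disagree. The example shows that the planned tables would omit the size and the upper limit of the excess. No conclusion of the trial turns on this, but the remedy is already in the SAP and costs little.

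**What to change.** In SAP 8.2.6 and Tables 32 to 34, add at D28V the placebo-minus-azithromycin risk difference with its Miettinen-Nurminen 95% interval for each event type. Keep the event groupings of those tables and Table 34's restriction to subjects not hospitalised at enrolment. State that any excess harm on placebo is read from the upper bound of that interval. Keep the odds ratio and Fisher's test, as the protocol asks, and report the odds-ratio interval as not estimable when a cell is zero. D11V needs no new analysis, because Table 44 already plans risk differences there.

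The cost is a few lines of SAP text and one extra column in three supportive tables, with Table 36 as the template. The protocol's requests are still met, so no amendment is needed.

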8.2.7. Improvement in LRTI Symptoms at D11V and D28V Using ATP Analysis Populations

Separately for D11V and D28V, using ATP-11 and ATP-28, respectively, the proportions of subjects exhibiting improvement in at least one presenting symptom by D11V or by D28V will be computed for placebo versus azithromycin, in addition to an estimated odds ratio and its associated 95% CI. The significance of the difference in proportions will be tested by a Fisher's Exact Test. The analysis will be repeated, analyzing each symptom individually and results will be provided in [Table 35](#) and [Table 36](#). The Wald method will be used for calculating 95% CI for odds ratio. A listing of all LRTI symptoms is provided in [Listing 17](#).

8.2.8. Analysis of DOOR at D5V Using ITT and ATP-5 Analysis Populations

DOOR at D5V is defined in Section 3.3.

The null hypothesis corresponding to this analysis is:

H0: The sum of the probability that a subject assigned to placebo will have a higher DOOR at D5V Visit than if assigned to the Azithromycin plus one-half the probability of equal DOORs at D5V is 50% (i.e., no difference in DOOR at D5V).

The above null hypothesis can be tested using a Mann-Whitney U Test.

This analysis will use multiple imputation with a linear model to impute missing DOOR at D5V. Details of multiple imputation methods are described in Section 8.4.2.

For each of the 20 complete multiple imputation datasets, a Mann-Whitney U statistic will be computed using randomization to placebo versus randomization to azithromycin to define the binary grouping and DOOR at D5V as the outcome. The U statistics are asymptotically normal distributed, and so they can be combined into a single test statistic using Rubin's Rules [3].

Defining the following:

n_1 : number of subjects in ITT population randomized to placebo

n_2 : number of subjects in ITT population randomized to Azithromycin

m : number of imputed datasets ($m = 20$)

Q_i : U statistic computed from the i^{th} multiply imputed dataset

$$\bar{Q} = \frac{1}{m} \sum_{i=1}^m Q_i$$

Q_0 : the expected value of a U statistic under the null hypothesis ($Q_0 = \frac{n_1 n_2}{2}$)

\bar{U} : The within imputation variance (this is not the mean of the U statistics). Correcting for ties, the formula for the within imputation variance of the Mann-Whitney U statistic is:

$$\bar{U} = \text{Var}(Q_i) = \frac{n_1 n_2}{12} \left[(n_1 + n_2 + 1) - \frac{1}{(n_1 + n_2)(n_1 + n_2 + 1)} \sum_{c=1}^D (M_c^3 - M_c) \right]$$

[2 and 4]

where M_c is the number of tied ranks for the c^{th} value DOOR in the dataset and D is the number of distinct values of DOOR in the dataset. Because the numbers of tied ranks should be very similar across the 20 multiply imputed datasets, the number of ties will be counted from the first imputed dataset only, and those counts will be used to compute the corrected variance.

$$B = \frac{1}{m-1} \sum_{i=1}^m (Q_i - \bar{Q})^2$$

$$T = \bar{U} + \frac{m+1}{m} B$$

$$W = \frac{(\bar{Q} - Q_0)^2}{T}$$

$$r = \frac{m+1}{m} \frac{B}{\bar{U}}$$

$$\nu = (m-1) \left(1 + \frac{1}{r} \right)^2$$

Under null hypothesis corresponding to the secondary DOOR analysis of this study,

$$W \sim F_{1,\nu}$$

This F-distribution is used to compute a p-value (one-sided probability) from the overall test statistic W . The null hypothesis will be rejected if $p < 0.05$.

A corresponding 95% CI for U will be computed using the overall test statistic W through the inversion of the F-test. Dividing the bounds of this CI by $n_1 n_2$ will yield the bounds for the 95% CI of $\text{Pr}(\text{Higher DOOR in placebo}) + 0.5 \text{Pr}(\text{Equal DOOR in azithromycin})$. Thus, the CI for DOOR probability is given by:

$$95\% \text{ CI: } \left(\frac{\bar{Q} - \sqrt{T \times F_{0.95,1,\nu}}}{n_1 n_2}, \frac{\bar{Q} + \sqrt{T \times F_{0.95,1,\nu}}}{n_1 n_2} \right)$$

A point estimate of the DOOR probability will be obtained by dividing \bar{Q} by $n_1 n_2$. Results will be shown in [Table 37](#) for ITT population.

Analysis of DOOR will be repeated for the ATP-5 analysis population and using the same multiple imputation model as ITT analysis. Results of this analysis will be reported in [Table 38](#).

Additional analyses of DOOR at D5V will be performed using only subjects in the ATP-5 population with complete data. These analyses will test the null hypotheses described above using the Mann-Whitney U Test, estimate $\Pr(\text{Higher DOOR in placebo}) + 0.5 \Pr(\text{Equal DOOR})$ using U divided by the number of pairwise comparisons, and will compute confidence intervals by (1) inverting the Mann-Whitney U Test and (2) using a non-parametric bootstrap.

Confidence intervals from inverting the Mann-Whitney U Test will be given by:

$$\left(\frac{U}{n_1 n_2} - 1.96 \times \sqrt{\frac{\text{Var}(U)}{(n_1 n_2)^2}}, \frac{U}{n_1 n_2} + 1.96 \times \sqrt{\frac{\text{Var}(U)}{(n_1 n_2)^2}} \right)$$

Correcting for ties, the formula for the variance of U is:

$$\text{Var}(U) = \frac{n_1 n_2}{12} \left[(n_1 + n_2 + 1) - \frac{1}{(n_1 + n_2)(n_1 + n_2 + 1)} \sum_{c=1}^D (M_c^3 - M_c) \right]$$

where M_c is the number of tied ranks for the c^{th} value DOOR in the dataset and D is the number of distinct values of DOOR in the dataset.

Confidence intervals for the DOOR probability using a non-parametric bootstrap:

$$\left(\frac{U_{0.025}}{n_1 n_2}, \frac{U_{0.975}}{n_1 n_2} \right)$$

Where $U_{0.025}$ and $U_{0.975}$ are chosen as the 250th and 9750th values in a sorted array of 10000 values of Mann Whitney U statistics generated from random resampling (number of values sampled to generate the statistic will be equal to the number of subjects in the respective analysis population) of the empirical distributions of DOOR scores in each treatment arm for the given analysis population.

Results from the analysis using ATP-5 population with complete data will be reported in [Table 48](#).

Summaries of OCO, a component of DOOR will also be analyzed. Number and percentage of subjects in each OCO category at D5V along with its 95% CI calculated using the Wilson method will be presented in [Table 49](#) for the ITT analysis population, [Table 50](#) for ATP-5 analysis population, and graphically in [Figure 16](#). A cumulative distribution function of these OCOs at D5V will also be presented in [Figure 17](#) for the ITT analysis population and [Figure 18](#) for the ATP-5 analysis population. An individual listing of observed values of DOOR is provided in [Listing 16](#).

